## **6.2 Criteria for Removal from Study**

### **Withdrawal Visit/Discontinuation of Therapy**

In the absence of treatment delays due to adverse events, treatment may continue for 12 weeks or until one of the following criteria applies:

- Patient misses more than four consecutive weeks of escitalopram.
- Intercurrent illness that prevents further administration of treatment or patient inability to swallow escitalopram/placebo capsules,
- The investigator considers it, for safety reasons, to be in the best interest of the patient.
- Unacceptable adverse event(s):

-NCI CTCAE version 5.0 Grade 2 or higher hemorrhage that occurs within the first four weeks of treatment  
-NCI CTCAE version 5.0 Grade 4 suicidal ideation  
-NCI CTCAE version 5.0 Grade 3 or higher mania  
-NCI CTCAE version 5.0 Grade 4 hyponatremia

Patients who experience severe depression will be referred to a psychiatrist. They will also continue, if agreeable, on the study and with scheduled surveys according to the defined schedule (QIDS, PHQ-9, FACT-Hep, FIBSER).

Patients will be withdrawn if they are deemed at high risk for suicide or if they wish to voluntarily withdraw from the study.

- Patient decision to withdraw from treatment (partial consent) or from the study (full consent),
- Pregnancy during the course of the study
- Death

- The Principal Investigator and/or the Case Comprehensive Cancer Center Data Safety Toxicity Committee (DSTC) reserve the right to temporarily suspend or prematurely discontinue this study if unacceptable study-related risks are identified. The date and reason for discontinuation must be documented. Every effort should be made to complete the appropriate assessments.

## **Handling of Participant Withdrawals and Participant Discontinuation of Study Intervention**

Patients who withdraw from treatment will have an end of study visit as described in Section 6.3. They will continue to be followed with surveys at the scheduled intervals and for cancer-specific outcomes, unless patients refuse this follow-up by withdrawal of consent.

### **6.3 Duration of Follow-Up**

#### **End of Treatment Study Procedures**

An end of treatment visit will be conducted on Day 85 (Week 13). This will be a clinic visit and will include a physical exam, collection of pill diary and any unused pills, toxicity assessment, QIDS-SR, PHQ-9, Fact-Hep and FIBSER. The patient's disease and treatment status will also be assessed.

During Week 25 (12 weeks after the end of treatment), a phone visit will be conducted which will include a toxicity assessment, QIDS-SR, PHQ-9, Fact-Hep and FIBSER. Patients who screen above 11 on the QIDS-SR or above 9 on the PHQ-9 will be referred by the study team to a social worker, who will then conduct their own assessment and make appropriate referrals to psychiatry if necessary. Patients who give an affirmative reply to Question 12 on the QIDS-SR or 9 on the PHQ-9 indicating thoughts of suicide, will be referred to Seidman Psychiatry Service for evaluation (please see Section 7.0).

#### **Post-treatment/Follow-Up**

Patients will call the research coordinator, their doctor, or the study PI if they experience depression-related symptoms.

#### **Long Term/Survival Follow-up**

After the Week 25 visit, cancer-specific information will be obtained for three years to assess disease and survival status. The information will be obtained every three months either by a review of the patients' medical record or by phone. Patients who undergo tumor resection after completion of the study will have tumor and blood samples collected for research studies.

### **7.0 Dose Delays/Dose Modifications**

The starting dose will be one pill (10mg of escitalopram/placebo) during Weeks 1 and 2 followed by two pills daily (20mg of escitalopram/placebo) during Weeks 3-10 then one pill (10mg of escitalopram/placebo) during Weeks 11-12. Drug toxicities will be assessed based upon responses to questionnaires and from entries on pill diaries every two weeks by the clinical staff during the scheduled phone calls or in-person visits. There will be no dose reductions. Drug will be discontinued for the Adverse Events of Special Interest (hemorrhage, suicidal ideation and mania)

and for Grade 4 hyponatremia as described in Table 7.1. Drug may also be discontinued, at the discretion of the treating physician, for other adverse events determined by the PI to be related to escitalopram/placebo. If the event takes place in the first four weeks of starting treatment, the patient will be removed from study and will not be followed.

Patients who discontinue drug for any reason will continue to complete all questionnaires as outlined on the Study Calendar. The study team will make every effort to ensure that patients stay on schedule.

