### **3.2 Number of Subjects**

The clinical trial is powered for 46 patients, including 23 patients in each arm (escitalopram and placebo). However, 55 patients will be enrolled, in order to achieve the desired number due to expected attrition both before and after initiation of therapy or due to removal from study due to reasons noted in Section 6.2.

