### **3.3 Replacement of Subjects**

Patients will not be replaced.

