#### Unblinding Procedures:

- Patients will be unblinded if study drug is discontinued for the Adverse Events of Special Interest (hemorrhage, suicidal ideation and mania) as described in Table 7.1.
- Patients will be unblinded if study drug is discontinued due to Grade 4 hyponatremia as described in Table 7.1.

- Patients will be unblinded if they meet the criteria for removal from study as defined in Section 6.2.
- Patients will be unblinded at the time of their Day 85 (Week 13) end of treatment visit.

Patients will be unblinded by IDS staff as outlined in the Unblinding Manual. Patients who are unblinded before they complete all study visits will be asked to continue to have study-related phone calls with study staff and complete all study-related questionnaires. Patients who are unblinded prior to the end of treatment visit and undergo tumor resection will be required to have the research tissue sample and post-surgery research blood samples taken.

An assessment of depression will be made by the treating physician. Based on the assessment, patients who received escitalopram may be given the option of continuing the medication either under the supervision of their medical oncologist or primary care provider. If this occurs, the patient will obtain escitalopram from commercial supply at the dose prescribed by the patient's medical oncologist, primary care physician or other provider.

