## **14.3 Sample Size Considerations**

The primary objective of this study is to obtain preliminary evidence of efficacy of the treatment in preventing incident moderate or greater depression defined as a QIDS-SR score greater than 11 at 12 weeks. Assuming 23 subjects per arm and a true rate of depression in the control arm of 40%, we have 80% power to detect a difference if the true rate in treatment arm is 13.8% using a one-sided alpha of 0.10. Assuming an observed rate of 40% in the control arm, the upper limit of the 80% confidence interval for the risk ratio ranges from 0.56 when the observed treatment arm rate is 10% to 1.09 when the observed treatment arm rate is 25%. Any patient who has less than 65% compliance rate after four weeks of escitalopram/placebo (as determined during bi-weekly pill diary review) will be considered not evaluable and will be replaced. Any patient who experiences a serious adverse event that requires discontinuation of study drug within the first four weeks of treatment will be considered not evaluable and will be replaced.

To achieve a final sample size of 46 (23 per arm) at 12 weeks we will randomize 55 patients allowing for up to 15% attrition.

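### Section 7.0 ends follow-up after an early event-driven drug stop, while its next paragraph and Section 6.1 keep the questionnaires going

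*Combined protocol and SAP*

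**What the plan says.** **Section 7.0** lists the reasons for stopping drug: the adverse events of special interest (hemorrhage, suicidal ideation, mania), Grade 4 hyponatremia and, at the physician's discretion, other drug-related events. It then says that if the event occurs in the first four weeks, "the patient will be removed from study and will not be followed". The next paragraph opens: "Patients who discontinue drug for any reason will continue to complete all questionnaires".

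**Section 6.1, Unblinding Procedures**, says "Patients will be unblinded if they meet the criteria for removal from study as defined in Section 6.2". Patients unblinded before finishing their visits "will be asked to continue to have study-related phone calls with study staff and complete all study-related questionnaires". One of the Section 6.2 criteria is "Grade 2 or higher hemorrhage that occurs within the first four weeks of treatment".

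**Section 14.3** handles an overlapping group differently. For SAEs, its rule is that anyone whose event "requires discontinuation of study drug within the first four weeks of treatment will be considered not evaluable and will be replaced". The sentence before it applies the same rule to patients below 65% compliance after four weeks. Section 3.3 says "Patients will not be replaced", and the Replacement Policy under Section 14.3 repeats this. Section 14.2 analyses all randomized patients as assigned and imputes missing dichotomous outcomes by multiple imputation, relying on MAR.

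**The concern.** Site staff can find opposite instructions for the same patient, and the choice decides whether the primary outcome is collected. The analysis includes everyone randomized. A patient who is not followed therefore stays in it only through an imputed week-12 value, after a stop that may have been caused by the drug. MAR is hardest to defend for this kind of missing value, and Section 14.2 does not say which variables the imputation uses. The loss is avoidable, because other parts of the protocol already ask these patients for the questionnaires. Section 14.3 adds a third handling that agrees with neither.

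**Working it through.** No calculation decides the point; the texts do. The arithmetic only gives a sense of size.

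**1. One patient, every rule.** Take a Grade 2 hemorrhage in week 3 with drug stopped.

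| Place | Instruction |
|---|---|
| Section 6.2, Table 7.1 | Remove from study |
| Section 6.1 | Unblind; ask for calls and all questionnaires |
| Section 7.0, four-week sentence (broad reading, step 2) | Remove; no follow-up |
| Section 7.0, next paragraph | Questionnaires continue |
| Section 14.2 | Stays in the analysis as randomized |
| Section 14.3, if the event is serious | Not evaluable; replaced |
| Section 3.3, Replacement Policy | No replacement |

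**2. Which events the sentence covers.** It comes straight after the discretionary stops, so two readings are possible.
- *Broad (all listed events):* it conflicts with the next paragraph of Section 7.0, and with Section 6.1 as in the table.
- *Narrow (discretionary stops only):* it still conflicts with the next paragraph, which covers stops for any reason. It conflicts with Section 6.1 only where the stop also meets a Section 6.2 criterion.

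**3. What is lost.** The study calendar schedules QIDS-SR after baseline on Days 8, 22, 36, 50, 64, 78 and 85, which is seven scores (the Section 14.2 model counts six without naming them). Only Days 8 and 22 fall within the first 28 days. With the 7-day window, the Day 36 contact cannot come before Day 29. An event recognised promptly therefore leaves up to two scores. An event on Day 25 first reported at the Day 36 call could leave a third.

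**4. Power and attrition.** Section 14.3 states 80% power for 40% versus 13.8% with 23 per arm at one-sided 0.10. The unpooled normal formula gives Φ[(0.40 − 0.138)/√(0.40×0.60/23 + 0.138×0.862/23) − 1.2816] = 79.3%. The pooled formula gives 77.5%, and exact enumeration of the pooled z-test gives 80.1%. The stated figure reproduces.

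For attrition, 46/(1 − 0.15) = 54.1, rounded up to 55. The room is 55 − 46 = 9 patients, or 9/55 = 16.4% (15% of 55 is 8.25). Section 3.2 says this allowance includes attrition "or due to removal from study due to reasons noted in Section 6.2". If early-event losses fit within it, planned power does not change.

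**5. Scale of a possible bias (every input is an assumption).** Suppose there is no true effect, with 40% depressed in both arms. An arm of N = 27 loses k patients, the other arm loses none, and imputation corrects nothing. Let f = k/N and let r be the lost patients' true week-12 risk. Then RR = [(0.40 − f·r)/(1 − f)]/0.40.

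| r | k = 1 | k = 2 |
|---|---|---|
| 20% | 1.02 | 1.04 |
| 40% | 1.00 | 1.00 |
| 60% | 0.98 | 0.96 |
| 80% | 0.96 | 0.92 |

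N = 28 gives the same values to two decimals. With 23 per arm at 40% in each, the standard error of log RR is √[2×0.60/(23×0.40)] = 0.36. The largest shift, |ln 0.92| = 0.083, is about 0.23 of that.

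**The case against.** **The four-week sentence may be a deliberate exception.** Four-week limits also appear in Section 6.2, Table 7.1 and Section 14.3, so early removal looks intended, and a specific rule can precede a general one. That is fair as to removal from drug. It does not rescue the no-follow-up clause: the general rule follows at once, covers any reason and carves nothing out, and Section 6.1 has no four-week exception. The Summary of Changes records that the Section 6.1 request to continue questionnaires was added in the April 2022 version, which suggests that continued collection was wanted. It is true that Section 6.1 only asks patients to continue.

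**The all-randomized analysis can still be run by imputation.** This stands: Section 14.2 is not literally contradicted by lost follow-up. Nor is the Section 6.2 paragraph on surveys after withdrawal from treatment, which need not cover removal by protocol.

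**Scores collected after unblinding may be coloured by knowing the assignment.** This also stands, but Section 6.1 already accepts it.

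**Stronger readings to avoid.** A reader might infer that the sentence biases the trial in favour of escitalopram, or that it costs power. The documents give no event rate, no outcome risk for these patients and no direction, and Section 3.2 counts Section 6.2 removals within the attrition allowance. A reader might also infer that two scores is a hard maximum; that assumes the event is discovered at once.

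**Conclusion.** Wrong as written: an internal inconsistency in current text. Section 7.0 contradicts its own next paragraph on either reading of which events it means, and contradicts Section 6.1 for any early stop that the sentence covers and that triggers unblinding there. Followed literally, it discards the week-12 primary outcome of some randomized patients and leaves it to MAR imputation.

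The practical effect is probably small. Its size and direction cannot be settled from the documents, and the risk ratios of 0.92 to 1.04 only illustrate one or two losses confined to one arm. The case for change rests on conflicting instructions and avoidable loss of primary data, not on a demonstrated bias. Section 14.3 is a related but separate conflict. It affects both early serious-event stops and low compliance, against Section 3.3, the Replacement Policy and the all-randomized analysis. This should be corrected, but it does not undermine the design.

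**What to change.** 1. **Section 7.0:** delete the no-follow-up clause. State once, so that it also governs Table 7.1 and Section 8.2.4, that removal from study after an adverse event means stopping study drug. Scheduled questionnaires and survival follow-up are still sought unless the patient withdraws consent or contact is clinically inappropriate. The last condition covers patients withdrawn for high suicide risk.
2. **Section 14.3:** remove the not-evaluable-and-replaced rule from both sentences, the early serious-event one and the 65%-compliance one. Correcting only the first would leave the section in conflict with Sections 3.3 and 14.2 and its own Replacement Policy.

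The cost is a short amendment: one deletion, one definition and two edited sentences. Drug-stopping thresholds stay as they are, and the questionnaires belong to contacts already on the study calendar.

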**Table 7.1 Criteria for dosing delays and re-initiation of treatment due to study drug-related toxicity**

CTCAE Grade* Patient report or from any assessment scale	Dose Discontinuation Guidelines	
Hemorrhage (any site)	Grade 1: Mild symptoms; intervention not indicated Grade 2: Moderate symptoms; intervention indicated Grade 3: Transfusion indicated; invasive intervention indicated; hospitalization Grade 4: Life-threatening consequences; urgent intervention indicated	Grade 2 or greater: Discontinue drug, inform treating physician and PI immediately upon discovery.  (if this happens within first 4 weeks remove patient from study)
Suicidal ideation**	Grade 1: Increased thoughts of death but no wish to kill oneself Grade 2: Suicidal ideation with no specific plan or intent Grade 3: Specific plan to commit suicide without serious intent to die which may not require hospitalization Grade 4: Specific plan to commit suicide with serious intent to die which requires hospitalization	Grade 1-3: inform treating physician immediately upon discovery Grade 4: discontinue drug and remove from study.  See Table 7.2
Mania	Grade 1: Mild manic symptoms (e.g., elevated mood, rapid thoughts, rapid speech, decreased need for sleep) Grade 2: Moderate manic symptoms (e.g., relationship and work difficulties; poor hygiene)	Grade 3-4: discontinue drug and remove from study, notify treating physician and PI immediately.

	Grade 3: Severe manic symptoms (e.g., hypomania; major sexual or financial indiscretions); hospitalization not indicated; new onset  Grade 4: Life-threatening consequences, threats of harm to self or others; hospitalization indicated	
Hyponatremia	Grade 1: <LLN - 130.0 mmol/L  Grade 2: 125-129 mmol/L and asymptomatic  Grade 3: 125-129 mmol/L symptomatic; 120-124 mmol/L regardless of symptoms  Grade 4: <120 mmol/L; life-threatening consequences	Grade 4: discontinue drug and remove from study.
*CTCAE Version 5.0		
**Please see safety guidelines section below regarding patients exhibiting suicidal ideation		

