There will be study-related clinic visits scheduled for Days 15 and 71. On Day 15, patients will be given pill bottles for Weeks 3-10. On Day 71, patients will be given pill bottles for Weeks 11-12. The Week 11-12 pill diary along with any unused pills will be collected at the end of treatment clinic visit (Week 13, Day 85). All other visits will be conducted via phone call from the study staff every two weeks beginning on Day 8. Phone visits will be conducted on Days 8, 22, 36, 50, 64 and 78 (+/- 7 days). However, if a patient's scheduled chemotherapy-related visit, clinic visit or hospital visit for any other reason happens to fall on (or within the 7 day window of) a planned study visit, the visit may be conducted in person with study staff. During these visits (phone or in-person), the study staff will perform a toxicity assessment and ask questions to determine if the patient is being compliant with taking the pills and completing the pill diary. The study staff member will verbally conduct the QIDS-SR, PHQ-9, and FIBSER with the patient and record the patient's answers and the FACT-Hep will be given directly to the patient to complete (if not done over the phone). The FACT-Hep will be performed monthly on Days 1, 22, 50 78, and 85.

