#### **8.2.4 Adverse Events of Special Interest**

The following adverse events must be recorded, evaluated, and reported according to reporting policies of the IRB of record. Procedures related to these events will be followed as noted in Tables 7.1 and 7.2. Events are graded using CTCAE v5.0.

- Serious bleeding event (Grade 2 or greater). Will prompt discontinuation of escitalopram or placebo and removal from study.
- Mania. Symptoms consistent with mania will prompt referral to psychiatry.
- Suicidal ideation. Patients will be evaluated for suicidal ideation every 2 weeks using the QIDS and referred to psychiatry if present.

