### **Treatment failures**

Patients with high risk for suicide, suicide attempts, or a score of  $\geq 16$  points on the QIDS-SR at 12 weeks will be considered “treatment failures” and will be provided referrals for more optimal depression treatment throughout the duration of the study. Patient scores and adverse events will be reviewed by clinical study staff (RN or MD) within 24 hours of collecting information from patients to determine if additional action is needed per Section 7. Cases of suspected suicidal ideation will be reviewed within four hours as noted in Section 7, and study staff will immediately take action as appropriate upon review.

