**Weeks #: 1 and 2 (Days 1-14)**

#### **INSTRUCTIONS FOR THE SUBJECT:**

1. You will take one 10mg capsule of escitalopram/placebo each day. You should take your pill in the morning or evening. You may take the pill with or without food, as you wish.
2. Record the date, the number of tablets you took, and what time you took them.
3. If you have any comments or side effects please record them in the “Comments” column below.
4. If you have bleeding, please record in the “Bleeding” column below.
5. Please bring your pill bottle and this form to your physician when you come for your next appointment.
6. Please sign your name at the bottom of the diary.

Date	Day	# of 10mg pills and time taken	Comments	Bleeding
				Type of bleeding: nose bleed, cut that won't stop bleeding, bruising, blood in urine, red or black stool, Other (please describe) State if: Mild, Moderate, Severe
	(Wk 1) 1			
	2			
	3			
	4			
	5			
	6			
	7			
	(Wk 2) 8			
	9			
	10			
	11			
	12			
	13			
	14			
Subject's Signature: _____		Date: _____		

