#### INSTRUCTIONS FOR THE SUBJECT:

1. You will take two 10mg capsules of escitalopram/placebo each day. You should take your pill in the morning or evening. You may take the pill with or without food, as you wish.
2. Record the date, the number of tablets you took, and what time you took them.
3. If you have any comments please record them in the "Comments" column below.
4. If you have bleeding, please record in the "Bleeding" column below.
5. Please bring your pill bottle and this form to your physician when you come for your next appointment.
6. Please sign your name at the bottom of the diary.

Date	Day	# of 10 mg pills and time taken	Comments	Bleeding Type of bleeding: nose bleed, cut that won't stop bleeding, bruising, blood in urine, red or black stool, Other (please describe) State if: Mild, Moderate, Severe
	(Wk 3) 15			
	16			
	17			
	18			
	19			
	20			
	21			
	(Wk 4) 22			
	23			
	24			
	25			
	26			
	27			
	28			
	(Wk 5) 29			
	30			
	31			
	32			
	33			
	34			
	35			
	(Wk 6) 36			
	37			
	38			
	39			
	40			
	41			
	42			

Subject's Signature: \_\_\_\_\_ Date: \_\_\_\_\_

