## APPENDIX VI

### FIBSER Scale

#### FIBSER Scale

Please choose and circle your response based on side effects that you believe are caused by medications for depression **IN THE PAST WEEK**.

Do **NOT** rate side effects if you believe they are caused by medications for medical conditions other than depression.

1. IN THE PAST WEEK, how **much of the time** did you experience side effects caused by medications for depression?

0	1	2	3	4	5	6
None of the time (no side effects)	10% of the time	25% of the time	50% of the time	75% of the time	90% of the time	All the time

2. IN THE PAST WEEK, how **severe** were the side effects to your medications for depression?

0	1	2	3	4	5	6
None (no side effects)	Minimal severity	Mild severity	Moderate severity	Marked severity	Severe severity	Intolerable severity

3. IN THE PAST WEEK, how much have the side effects to your medications for depression **interfered** with your day-to-day activities?

0	1	2	3	4	5	6
No interference with activities	Minimal interference with activities	Mild interference with activities	Moderate interference with activities	Marked interference with activities	Severe interference with activities	Unable to function

Clinical Relevance: Question 3	
0 – 2	No changes needed.
3 – 4	Side effects should be addressed.
5 – 6	Change treatment.

Adapted by [name] ([contact])  
with permission from Wisniewski SR et al, J Psychiatr Pract 2006;12:71-9.

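### The pill diary sends a bleed that may require stopping drug to the next appointment, with no prompt to call

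*Combined protocol and SAP*

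**What the plan says.** Bleeding of Grade 2 or above is a mandatory stop. The hemorrhage row of Table 7.1 reads "Grade 2 or greater: Discontinue drug, inform treating physician and PI immediately upon discovery", and Section 8.2.4 lists "Serious bleeding event (Grade 2 or greater). Will prompt discontinuation of escitalopram or placebo and removal from study". Under Section 6.1, stopping drug for such a bleed also triggers unblinding.

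Section 7.0 gives the detection method: "Drug toxicities will be assessed based upon responses to questionnaires and from entries on pill diaries every two weeks", at scheduled calls or visits. Section 6.1 sets the calls: "Phone visits will be conducted on Days 8, 22, 36, 50, 64 and 78 (+/- 7 days"). Clinic visits fall on Days 1, 15, 71 and 85.

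The diary in Appendix II has a bleeding column for type and for a Mild, Moderate or Severe rating. Its instructions on bleeding and on returning the form are the same on all four pages: "If you have bleeding, please record in the" bleeding column, and "Please bring your pill bottle and this form to your physician when you come for your next appointment".

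Section 14.2 (Treatment failures) has staff review scores and adverse events "within 24 hours of collecting information from patients to determine if additional action is needed per Section 7".

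**The concern.** Every stopping rule waits for discovery, so Table 7.1 itself is not at fault. The weakness is in the route by which a bleed is discovered. The one form built to capture it tells the patient to write it down and bring it along later. The diary's Moderate rating also resembles Table 7.1's description of Grade 2 (moderate symptoms needing intervention). A patient could record a likely stopping event, follow every diary instruction and alert nobody until the next contact.

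In that case a patient who may have met the protocol's stopping criterion goes on taking blinded capsules, two a day in Weeks 3-10. This is a matter of patient safety and does not touch the efficacy comparison.

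**Working it through.** **1. Is there another prompt?** Each patient-completed form and each instruction to make contact was checked for bleeding.

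| Source | Bleeding item or prompt to call about bleeding? |
|---|---|
| QIDS-SR (Appendix IV) | No item |
| FACT-Hep (Appendix V) | No item |
| FIBSER (Appendix VI) | No item; the patient is told not to "rate side effects if you believe they are caused by medications for medical conditions other than depression" |
| PHQ-9 (Appendix VII) | No item |
| Pill diary, four pages (Appendix II) | Bleeding column; none of the six instructions says to call |
| Section 6.3, Post-treatment | Call for depression-related symptoms only |
| Section 8.2.1 | Contact the PI if a symptom becomes debilitating; bleeding not named |
| Section 14.2, 24-hour review | Clock starts when information is collected, not at onset |

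**2. The plan's own interval.** The phone days are 8, 22, 36, 50, 64 and 78. Successive differences are 14, 14, 14, 14 and 14 days, which reproduces the two-weekly interval in Section 7.0.

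**3. Lag in Weeks 3-10, all study contacts counted.** Contacts on Days 15, 22, 36, 50, 64 and 71 give gaps L of 7, 14, 14, 14 and 7 days, 56 in total. If onset is uniform over the period and the bleed surfaces only at the next contact:

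- Mean lag = Σ(L²/2) / ΣL = (24.5 + 98 + 98 + 98 + 24.5) / 56 = 343 / 56 = 6.125 days.
- At two capsules a day: 6.125 × 2 = 12.25 capsules.
- Longest lag: 14 days, or 28 capsules.
- Share of onset days waiting more than 7 days: (3 × 7) / 56 = 21 / 56 = 37.5%.

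Counting in whole days gives a mean of 5.6 if a same-day contact catches the bleed, and 6.6 if only a later day's contact does.

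**4. Lag in Weeks 3-10, scheduled toxicity assessments only.** The Study Calendar ticks no toxicity assessment on Day 15 or Day 71, so the contacts are Days 22, 36, 50, 64 and 78. For onsets over Days 15-71:

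- Mean lag = (7 × 3.5 + 42 × 7 + 7 × 10.5) / 56 = (24.5 + 294 + 73.5) / 56 = 392 / 56 = 7.0 days.
- Share waiting more than 7 days: (21 + 7) / 56 = 50%.
- Longest lag: still 14 days.

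**5. Whole treatment period, all contacts.** Days 1, 8, 15, 22, 36, 50, 64, 71, 78 and 85 give six gaps of 7 days and three of 14. Mean lag = (6 × 24.5 + 3 × 98) / 84 = 441 / 84 = 5.25 days.

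**6. Effect of the visit window.** If the Day 22 call is made 7 days early and the Day 36 call 7 days late, the gap is (36 + 7) − (22 − 7) = 28 days. That is an outer bound. In a simulation with call dates uniform within their windows and the Day 15 and Day 71 visits fixed, the mean lag in Weeks 3-10 was about 7.5 days. Uniform call dates are an assumption.

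**The case against.** The strongest reply is that a bleed has several other ways to surface. Section 8.2.1 says patients are educated about symptoms and are under clinical care while on chemotherapy. Table 7.1 accepts a patient's report. Staff ask about toxicity at the scheduled contacts. The diary's reference to the next appointment could include a chemotherapy visit, which may come before the next study contact. The consent pages are not available and may say whom to call. A bleed needing intervention in a patient under oncology care will often be noticed, and Grade 3-4 bleeds would normally reach clinicians anyway.

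Much of this stands. These routes narrow the problem to a Grade 2 bleed that is neither volunteered nor seen elsewhere, and the lag figures apply only to that subset. They describe the contact calendar rather than risk. With 1:1 randomization about half of the patients take placebo, so capsule counts are not escitalopram exposure. Table 7.1 is headed as covering drug-related toxicity, and Section 8.2.3 leaves attribution to a physician, so a patient's own rating does not by itself establish that the criterion is met. No harm from a few more days of dosing has been shown.

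None of it closes the gap. The contact instruction in Section 8.2.1 is limited to debilitating symptoms, which a Grade 2 bleed need not be. Grading and attribution cannot begin until staff know of the bleed. If the consent form does carry a call instruction, repeating it on the page the patient fills in when bleeding occurs would still be useful.

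**Conclusion.** The concern holds as an inexpensive safety improvement. It is not a flaw in the stopping rule or in the analysis. The protocol makes a Grade 2 or greater bleed a mandatory stop, yet the diary defers reporting to the next appointment and no other form in the protocol asks about bleeding.

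For a bleed found only at the next study contact in Weeks 3-10, on nominal dates, the mean lag is 6.1 to 7.0 days, depending on whether the Day 15 and Day 71 visits count. The maximum is 14 days. Over the whole treatment period, counting every contact, the mean is 5.25 days. The visit windows allow 28 days at the extreme.

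These figures assume uniform onset, and a bleed that is neither volunteered nor seen at a chemotherapy or other visit. Patients seen more often will have shorter lags. Without a bleeding rate in the protocol, the number of patients affected cannot be estimated.

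**What to change.** Add one line to each of the four diary pages in Appendix II, and the same message to the Day 1 teaching in Section 6.1: *If you mark bleeding as Moderate or Severe, phone the study team the same day; do not wait for the next call.*

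Staff then grade the bleed by CTCAE, the investigator assigns attribution under Section 8.2.3, and Table 7.1 is applied unchanged. The patient's rating prompts the call and does not by itself stop drug. If the consent form already gives this instruction, repeat it on the diary.

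The cost is four diary lines, one protocol sentence and a few extra phone calls, some of them for bleeds that prove to be Grade 1.
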